# Examining the Impact of Photobiomodulation (PBM) on Brain Function in Dementia – Protocol

Protocol Summary	
Study Objectives:	
 
1. Replicate the findings of Saltmarche et al. (2017) on the effects of PBM treatment on cognitive function in older adults with dementia.
 
2. Examine whether 12 weeks of PBM therapy with the Vielight Neuro device improves default mode network (DMN) functional connectivity and cerebral blood flow (CBF) in older adults with dementia.
 
3. Examine the effects of PBM treatment on quality of life in older adults with dementia and on caregiver burden.
 

Study Design:	Randomized, wait-list controlled trial
Study Duration:	25 weeks
Number of Study Subjects:	10 patients with dementia and their primary caregivers
Main Inclusion Criteria:	
Primary Study Participants (PP):
 
 
• Diagnosis of dementia, preferably Alzheimer's dementia
 
• 50 years of age or older
 
• English language fluency
 
• No contraindications for MRI
 
• Has legally authorized representative (LAR) consent
 
 
Caregivers (CG):
 
 
• Currently provides care for PP
 
• Ability to answer questions about PP's behaviors, quality of life, and own stress levels
 

Summary of Study Procedures:	Ten pairs of older adults with dementia and their caregivers will be enrolled in a randomized, wait-list control trial. Five primary participants, PP, (i.e., individuals with dementia) will be randomized to start PBM treatment immediately with the Vielight Neuro device after the baseline psychometric and MRI assessments. Five PP will be randomized to a "Delayed PMB" group that will not start treatment with the Vielight Neuro device until after the 12-week psychometric and MRI assessment. Cognitive function and quality of life will be assessed in all PPs at baseline, weeks 6, 12, 18, and 24. Caregiver burden, positive aspects of caregiving, depressive symptomology, and dementia-related behaviors in the PP will be assessed in all caregivers (CG) at baseline, weeks 6, 12, 18, and 24. Neuroimaging measures will only be assessed in PPs at baseline and week 12.
Study intervention:	The experimental intervention will be PBM treatment with the Vielight Neuro device. The device uses clusters of 3 light emitting diodes (810nm wavelength). Diodes are placed on the skull at equidistance as well as intranasally to target different brain areas relevant to dementia. No significant heat is generated. PPs will be treated in 20 min sessions once daily, 5 days/week for at least 12 weeks. CG will be taught to use the device at home and maintain a treatment log/diary.
Study Aims:	1) Replicate Saltmarche et al. (2017)'s finding that 12 weeks of PBM

	
therapy improves cognitive function in patients with dementia.
 
 
2. Examine the effect of 12 weeks of PBM therapy on DMN functional connectivity and cerebral blood flow in individuals with dementia.
 
3. Examine the effects of 12 weeks of PBM therapy on quality of life in individuals with dementia and caregiver burden.
 
4. Determine if changes in cognition and quality of life are associated with changes in DMN functional connectivity and cerebral perfusion after 12 weeks of PBM therapy.
 

Study Hypotheses:	
1) Primary participants (PP) randomized to in the Immediate PBM group will show improvements in cognitive function after 12 weeks of near-infrared PBM therapy with the Vielight Neuro device compared to PP randomized to the Delayed PBM group.
 
2) PP randomized to the Immediate PBM group will show increased functional connectivity within nodes of the DMN after 12 weeks of near-infrared PBM therapy with the Vielight Neuro device compared to PP randomized to the Delayed PBM group.
 
3) PP randomized to Immediate PBM will show increased cerebral perfusion after 12 weeks of near-infrared PBM therapy with the Vielight Neuro device compared PP randomized to the Delayed PBM group.
 
4) Improvements in cognitive function (Alzheimer's Disease Assessment Scale-cognitive subscale, ADAS-cog, and the Montreal Cognitive Assessment, MOCA) and Quality of Life in Alzheimer's Disease (QOL-AD) scores will be correlated with increases in DMN functional connectivity and increases in cerebral perfusion after 12 weeks of PBM therapy with the Vielight Neuro in PP randomized to Immediate PBM
 
5) Caregivers in the Immediate PBM group will experience greater reductions in caregiver burden (Caregiver Burden Inventory, CBI) and depressive symptomology and improvements in positive feelings about caregiving (Positive Aspects of Caregiving) after 12 weeks compared to caregivers in the Delayed PBM group.

Statistical Methodology:	
We will use a two sample t-test on the baseline vs. week-12 differences in PP cognitive measures to examine between-group differences to test hypothesis 1.
 
A functional connectivity analysis produced coefficients from a priori defined seed-voxel correlation with Pearson correlation analysis will be used. Fisher's r-to-z transformation will be used to convert correlation maps into z maps. Random effect models will be applied for second level analysis. A two sample t-test on the baseline vs. week-12 differences between the Immediate PBM and Delayed PBM groups (Immediate [baseline-week 12] vs. Delayed [baseline-week 12]) will be used to examine the difference between the two groups for hypothesis 2.
 
We will extract the average cerebral blood flow (CBF) values for each subject by averaging the CBF values within a priori regions of interest (ROIs). Next, we will use a two sample t-test on the baseline vs. week-12 differences between the Immediate PBM and Delayed PBM groups

(Immediate [baseline-week 12] vs. Delayed [baseline-week 12]) to examine between-group differences for hypothesis 2. We will use Spearman's rank correlation analysis to examine the relationship between baseline-to-week 12 changes in DMN functional connectivity and CBF with baseline-to-week 12 changes in ADAS-cog, MOCA, and QOL-AD in the Immediate PBM group to test hypothesis 3. We will use a two sample t-test on the baseline vs. week-12 differences in CG measures (i.e., Caregiver Burden Inventory, Positive Aspects of Caregiving Scale, Geriatric Depression Scale) to examine between-group differences to test hypothesis 5. We will also evaluate the magnitude of treatment effects on the PP and CG psychometric measures using Cohen d effect sizes for the within-group difference in the Delayed PBM group (baseline-to-week 12 and week 12-to-week 24).

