## VII. Study Overview:

Photobiomodulation (PBM) is a kind of light therapy that uses red or near-infrared light to stimulate, heal, regenerate, and protect tissue that has either been injured, is degenerating, or else is at risk of dying. Human cadaver studies have shown near-infrared wavelengths can penetrate 40-50 mm through the scalp and skull. Saltmarche et al. (2017) recently showed that 12-weeks of transcranial treatment with a commercially available PBM device (i.e., the Vielight "Neuro") benefits cognitive function in patients with mild-to-moderately severe dementia. Specifically, Saltmarche et al. (2017) reported improvements on the Mini Mental State Examination (MMSE,  $p<0.003$ ) and Alzheimer's Disease Assessment Scale-cognitive subscale (ADAS-cog,  $p<0.03$ ) in 5 dementia patients after 12-weeks of PBM treatment. Because it is important to show that these promising preliminary findings are not spurious findings, the first objective of this study is to replicate Saltmarche et al's findings that the effects of 12-weeks of PBM treatment can improve cognitive function in older adults with dementia. Because the Vielight Neuro device targets nodes of the default mode network (DMN), which is dysregulated in dementia (e.g., Alzheimer's disease (AD)), second aim of this pilot study is to investigate whether 12 weeks of PBM therapy with the Vielight Neuro device improves DMN connectivity in older adults with dementia. Because there is suggestive evidence that PBM therapy enhances blood flow, the third study aim will examine whether 12-weeks of PBM therapy improves cerebral blood flow (CBF) in older adults with dementia. The final study aim is to investigate the effects of PBM treatment on quality of life in older adults with dementia and on caregiver burden.

Ten pairs of older adults with dementia and their caregivers (CG) will be enrolled in a randomized, wait-list control trial. Five primary participants, PP, (i.e., individuals with dementia) will be randomized to start PBM treatment immediately with the Vielight Neuro device after the baseline psychometric and

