MRI assessments. Five PP will be randomized to a "Delayed PMB" group that will not start treatment with the Vielight Neuro device until after the 12-week psychometric and MRI assessment. Cognitive function and quality of life will be assessed in all PPs at baseline, weeks 6, 12, 18, and 24. Caregiver burden, positive aspects of caregiving, depressive symptomology, and dementia-related behaviors in the PP will be assessed in all CGs at baseline, weeks 6, 12, 18, and 24. Neuroimaging measures will only be assessed in PPs at baseline and week 12.

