- Quality of life (Quality of Life Scale in Alzheimer's Disease, QOL-AD). The Quality of Life Scale in Alzheimer's Disease (QOL-AD) is a standard quality of life measure that asks parallel questions of affected individuals and caregivers and was used in our pilot study. Current quality of life is rated as poor (1 point), fair (2 points), good (3 points) or excellent (4 points) in 13 areas: physical health, energy, mood, living situation, memory, family, marriage, friends, self as a whole, ability to do chores around the house, ability to do things for fun, money, and life as a whole. Scores may range from 13 to 52 with higher scores reflecting better quality of life. Prior studies have found that the QOL-AD is a valid and reliable measure, with Cronbach's alpha of 0.84 for patient reports and 0.86 for caregiver reports and interrater reliability based on Cohen's kappa values >0.70.

Baseline Assessments in CGs:

- Caregiver burden (Caregiver Burden Inventory, CBI). The Caregiver Burden Inventory (CBI) is a standard measure that includes 24 items and 5 domains. Caregivers are asked to rate how often each statement describes their feelings (never, rarely, sometimes, quite frequently, nearly always). The total score may range from 0 to 96 with higher scores reflecting greater feelings of burden. The CBI has good internal consistency (Cronbach's alpha, 0.73-0.86), and it was sensitive to change in our pilot study.
- Participant quality of life (QOL-AD). As described above, the QOL-AD is a standard quality of life measure that asks parallel questions of affected individuals and caregivers and was used in our pilot study.
- Neuropsychiatric Inventory (NPI). Caregivers will also complete the NPI, which assesses the frequency, severity and level of distress caused by 12 common dementia-related behaviors (delusions, hallucinations, agitation/aggression, depression/dysphoria, anxiety, elation/euphoria, apathy/indifference, disinhibition, irritability/lability, aberrant motor behavior, sleep and appetite/eating). The NPI has good test-retest reliability (0.79-0.86) and good internal consistency (Cronbach's alpha, 0.87-0.88).
- Positive Aspects of Caregiving Scale is a standard measure that asks caregivers to rate their agreement/disagreement with 11 statements about positive aspects of caregiving on a 5-point Likert scale (disagree a lot ... agree a lot).

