- Geriatric Depression Scale (GDS) short form assesses depressive symptoms in caregivers based on self-report. The GDS short form is a 15-item yes/no scale that is valid in people with and without dementia

Follow-Up Psychometric Assessments (PPs and CGs separately). Follow-up assessments will be performed at weeks 6,12, 18, and 24 for all PPs and CGs. The procedures and measures will be identical to those at baseline.

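### Quality of life is a stated objective and QOL-AD is collected in both arms at baseline and week 12, but no planned between-group analysis includes it

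*Combined protocol and SAP*

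**What the plan says.** Quality of life is a stated target in four places. The Protocol Summary lists it under Study Objectives ("Examine the effects of PBM treatment on quality of life in older adults with dementia and on caregiver burden") and under Study Aims ("Examine the effects of 12 weeks of PBM therapy on quality of life in individuals with dementia and caregiver burden"). Section VIII repeats the aim, and section VII says: "The final study aim is to investigate the effects of PBM treatment on quality of life in older adults with dementia".

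The data are collected in both arms. Section VII states: "Cognitive function and quality of life will be assessed in all PPs at baseline, weeks 6, 12, 18, and 24". Section XIV has caregivers complete QOL-AD as well, because the instrument "asks parallel questions of affected individuals and caregivers and was used in our pilot study". On scoring it says: "Scores may range from 13 to 52 with higher scores reflecting better quality of life". On follow-up at weeks 6, 12, 18 and 24 for participants and caregivers it says: "The procedures and measures will be identical to those at baseline".

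QOL-AD appears by name in one analysis. The Statistical Methodology of the Protocol Summary correlates changes in connectivity and blood flow with "baseline-to-week 12 changes in ADAS-cog, MOCA, and QOL-AD in the Immediate PBM group". The same text plans Cohen d values for treatment effects on the participant and caregiver psychometric measures, within the Delayed group, from baseline to week 12 and from week 12 to week 24. QOL-AD falls under that description without being named. The Statistical Analysis Plan section mentions neither QOL-AD nor Cohen d.

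**The concern.** Section VIII pairs quality of life with caregiver burden in a single aim. Burden then receives a hypothesis (number 5) and, in the summary, a between-group test. Quality of life receives neither: none of the five hypotheses states a between-group effect on it.

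If the plan is followed as written, the trial reports on this objective with one single-arm correlation and single-arm effect sizes, although it randomised dyads and measured QOL-AD in both arms. There is also room for selection after the data are seen. QOL-AD has two raters and four follow-up visits, and no text says which version or time point addresses the objective.

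**Working it through.** **Step 1: scores against between-group analyses.** Section XIV lists eight psychometric scores, three from participants and five from caregivers.

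| Score | Between-group analysis | Where |
|---|---|---|
| MOCA | yes | summary and SAP section (cognitive measures) |
| ADAS-cog | yes | summary and SAP section |
| QOL-AD, participant | none | – |
| Caregiver Burden Inventory | yes | summary |
| QOL-AD, caregiver | none | – |
| NPI | yes | SAP section (repeated-measures ANOVA) |
| Positive Aspects of Caregiving | yes | summary |
| Geriatric Depression Scale | yes | summary |

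Six of the eight have one in at least one text. The two without are the two versions of QOL-AD. The remaining between-group analyses concern connectivity and perfusion.

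**Step 2: can existing wording absorb QOL-AD?** The t-test on participants' cognitive measures does not: hypothesis 4 identifies cognitive function as ADAS-cog and MOCA and names QOL-AD separately. The t-test on caregiver measures does not: its list is introduced by i.e. and holds three scales, none of them QOL-AD.

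**Step 3: what the two summary analyses can show.** Spearman's coefficient uses ranks only. Adding the same constant to every QOL-AD change leaves the ranks, and so the coefficient, unchanged. The correlation therefore says nothing about the size or direction of the mean change.

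The Delayed-arm d values cover an untreated period (baseline to week 12) and a treated one (weeks 12 to 24). Setting them side by side removes a drift that is equal in both periods. It does not remove non-linear decline, practice or expectation effects. It is not a randomised comparison, and no formal contrast of the periods is planned. After week 12 the Immediate arm may continue treatment (section XV), so no protected untreated comparator remains.

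**Step 4: precision, in units of the SD of a 12-week QOL-AD change.** Inputs: 5 per arm (section X). The documents give no alpha, sidedness or SD for this score, so two-sided 5% is assumed.

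- Randomised contrast, 5 v 5: t(0.975, 8) × √(2/5) = 2.306 × 0.632 = 1.46 SD.
- The same at 4 v 4: t(0.975, 6) × √(2/4) = 2.447 × 0.707 = 1.73 SD.
- Difference between the two Delayed-arm periods, n = 5, uncorrelated changes of equal SD: t(0.975, 4)/√5 × √2 = 2.776/2.236 × 1.414 = 1.242 × 1.414 = 1.76 SD.
- For a correlation r between the two changes, the last figure is 1.242 × √(2(1 − r)). At r = −0.5, the value if the changes were pure independent measurement error sharing the week-12 score, it is 1.242 × √3 = 2.15 SD. It equals 1.46 SD at about r = 0.31.

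In scale points, for an assumed SD of change of 3, 5 or 7 on the 13–52 scale, the randomised half-width is 1.458 × 3 = 4.4, 1.458 × 5 = 7.3 or 1.458 × 7 = 10.2 points.

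**Step 5: power.** By the noncentral t distribution at 5 v 5, power is 0.20 at a true difference of 0.8 SD and 0.29 at 1.0 SD. Reaching 0.80 needs about 2.02 SD.

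**The case against.** The best defence is that the summary does plan a treatment-effect estimate that takes in QOL-AD. The Delayed-arm d values are described as measuring the magnitude of treatment effects on the psychometric measures, and section XIV lists both QOL-AD versions among those measures. The untreated first period serves as each dyad's own control. This stands: a reader might infer that QOL-AD is never analysed, or that the Delayed-arm values cannot separate treatment from time at all, and the documents do not support either reading. What the defence does not supply is a randomised estimate or a planned contrast of the two periods.

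A reader might also infer that the SAP section overrides the summary, leaving the objective with no analysis. No text says that it supersedes the summary. Its silence is also not specific to QOL-AD: the Spearman analysis and the tests of caregiver burden, positive aspects and depression are missing from it too. That is a separate point.

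Finally, this is a funding-limited, proof-of-concept study of 10 dyads with no quality-of-life hypothesis, and an added contrast will rarely reach significance. That is true and limits the weight of the point. It is not a reason to leave the contrast out, since the plan accepts the same 5 v 5 comparison for cognition, caregiver burden, connectivity and perfusion.

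**Conclusion.** The point holds: an objective stated in four places has no between-group analysis, although the data for one are collected in both arms. The gain from correcting it is a randomised estimate and protection against choosing a rater or visit afterwards. It would not produce a decisive test.

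On precision, the randomised contrast compares favourably with the two-period comparison (1.46 v 1.76 SD) under uncorrelated changes of equal SD. That advantage would vanish at a correlation of about 0.31 and grow with a negative correlation. The case for randomisation does not depend on it. The scale-point figures rest on assumed SDs, and the power figures on two-sided 5% with no dropout.

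The sponsor should make the change, at modest priority: safety and the cognitive comparison are unaffected.

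**What to change.** In both the Statistical Methodology of the Protocol Summary and the Statistical Analysis Plan section:

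- Add QOL-AD to the week-12 two-sample comparison of change from baseline (Immediate minus Delayed) already planned for other measures. Report it in scale points with a 95% CI, as an estimate. Define change as week 12 minus baseline so that a positive difference favours PBM.
- Name the main rater before data are seen and treat the other as supportive. Participant-rated is one reasoned choice, because section VII names quality of life as assessed in participants and the caregiver both applies the device and logs perceived changes (sections XVI and XVII). Section XIV gives similar reliability for the two (alpha 0.84 and 0.86), so this is a judgement; fixing it in advance is what matters.
- Label the Delayed-arm Cohen d values supportive and not a randomised comparison.

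The cost is a sentence or two in each text and two table rows, with no new data or visits. The downsides are two more comparisons (psychometric scores with a between-group analysis go from 6 to 8), a visibly wide interval, and expectation effects that remain for both raters because no sham is described.

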**X. Study Population and Sample Size:**

We will study 10 dyads/pairs of individuals with dementia and their caregivers for this pilot, proof-of-concept study. Five individuals with dementia will be randomized to start PBM treatment with the Vielight Neuro device immediately after baseline assessments (Immediate PBM). Five individuals with dementia will be randomized to the Delayed PBM group, which will not start PBM treatment with the Vielight Neuro device until after completing Week 12 assessments. The sample size was chosen because this is what can be supported with the REAC and Department of Radiology Seed Grant funds. Also, because the Saltmarche et al. (2017) pilot study suggested that cognitive gains achieved by the dementia patients cannot be maintained once PBM treatments are discontinued, we plan to offer the Vielight Neuro devices to primary study participants upon completion of all study procedures so that

they may continue to use. Thus the sample size is also limited by the cost of the Vielight Neuro device (\$875 for research).

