**XV. Randomization:** Dyads of PP and CGs be randomized into one of two groups. The Immediate PBM Group will begin treatment with the Vielight Neuro device upon completion of baseline assessments. Treatment will continue for at least 12 weeks. *Because results from Saltmarche et al. pilot study suggest that cognitive gains achieved by patients with dementia may not be maintained without continued PBM treatment, PPs/CGs randomized to the Immediate PBM group will have the option of continuing PBM treatment after completion of Week 12 assessments.* The Delayed PBM Group will not begin treatment with the Vielight Neuro device until after completion of week 12 assessments.

**XVI. Caregiver Device Training** -- Prior to starting the PBM treatments, the CG will be trained how to position the Vielight Neuro device on the PP, how to control, how to clean, and how to maintain the Vielight Neuro device in a single 30 minute session. This training session will either take place at the SF VAMC or at the location of the PP/CG's choice (e.g., their home).

**XVII. Treatment Diary/Log:** To encourage adherence to the home-treatment PBM regimen, CGs will be instructed to log each treatment in the "Daily Home Treatment Journal." CGs will also be instructed to

note changes in the participants' memory, other cognitive processes, and general health conditions in the journal, which will be reviewed at bi-monthly "check-in" calls with the research staff.

**XVIII. Confirmation of Correct Device Use** -- After the first week of treatment, a research staff member will confirm that the CG knows how to properly use and maintain the Vieelight Neuro device. During the "confirmation" appointment, the CG will be asked to demonstrate his/her understanding and ability to correctly place the device on the PP. Any errors will be noted by the study staff and the caregiver will be re-trained or corrected as necessary. The research study staff will also review the treatment diary with the CG to check treatment compliance and its recording. The CG and PP will be encouraged to ask any questions or provide comments on device use which will be noted by study staff.

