## **STATISTICAL ANALYSIS PLAN**

We will use a two-sample t-test on the baseline vs. week-12 differences in PP cognitive measures to examine between-group differences to test hypothesis 1: Primary participants (PP) randomized to in the Immediate PBM group will show improvements in cognitive function after 12 weeks of near-infrared PBM therapy with the Vielight Neuro device compared to PP randomized to the Delayed PBM group.

We will also use a repeated-measures analysis of variance (ANOVA) to analyze the between-group differences in the ADAS-cog and NPI, with time (baseline, 6-, and 12-weeks) as the within-subject factor.

A functional connectivity analysis produced coefficients from a priori defined seed-voxel correlation with Pearson correlation analysis will be used. Fisher's r-to-z transformation will be used to convert correlation maps into z maps. Random effect models will be applied for second level analysis. A two-sample t-test on the baseline vs. week-12 differences between the Immediate PBM and Delayed PBM groups (Immediate [baseline-week 12] vs. Delayed [baseline-week 12]) will be used to examine the difference between the two groups for hypothesis 2: PP randomized to the Immediate PBM group will show increased functional connectivity within nodes of the DMN after 12 weeks of near-infrared PBM therapy with the Vielight Neuro device compared to PP randomized to the Delayed PBM group.

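### Cohen d for within-group change in the five-dyad Delayed PBM group is planned with no small-sample correction, named standardiser or interval, so it will be biased away from zero and its imprecision will not show

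*Combined protocol and SAP*

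**What the plan says.** The Protocol Summary, under Statistical Methodology, ends with this plan for the patient (PP) and caregiver (CG) measures: "We will also evaluate the magnitude of treatment effects on the PP and CG psychometric measures using Cohen d effect sizes". The same sentence goes on to restrict it to "Cohen d effect sizes for the within-group difference in the Delayed PBM group (baseline-to-week 12 and week 12-to-week 24". Section X gives the number behind each value: "Five individuals with dementia will be randomized to the Delayed PBM group". Each patient is paired with one caregiver, so the caregiver measures also rest on five people.

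The two periods differ in treatment status. Section XV (Randomization) says: "The Delayed PBM Group will not begin treatment with the Vielight Neuro device until after completion of week 12 assessments". The baseline-to-week-12 value therefore describes untreated change, and the week-12-to-week-24 value describes change on treatment.

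The hypotheses about group differences are tested separately. For hypothesis 1 the SAP says: "We will use a two-sample t-test on the baseline vs. week-12 differences in PP cognitive measures to examine between-group differences". The SAP does not mention Cohen d. The documents nowhere state a small-sample correction, the SD that forms the denominator, or a confidence interval for any effect size.

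**The concern.** Cohen d divides a mean change by an SD estimated from the same few people. In very small samples that SD is often too low. Dividing by it pushes d away from zero on average, which is why a corrected version (Hedges g) exists. With five people the correction is not negligible.

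A d from five people also has a very wide sampling distribution, and a point value printed alone hides this. A reader who sees 0.80 will take it for a large effect, although the same data are compatible with no effect.

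Section VII presents the study as a check that an earlier result in 5 patients was not spurious. A measure of magnitude that is biased away from zero and shown without its uncertainty serves that purpose poorly.

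**Working it through.** The documents give no effect size, SD or power figure for these measures, so there is no figure of the plan's to reproduce. Section X explains the size of the study by funding: "The sample size was chosen because this is what can be supported with the REAC and Department of Radiology Seed Grant funds".

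**Inputs**
- n = 5 in the Delayed PBM group (section X), so one SD has 5 - 1 = 4 df.
- Denominator: not stated. Three candidates are checked: the SD of change, the baseline SD, and the SD pooled over the two visits.
- Assumption: normally distributed scores.

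**Bias with one SD on 4 df**

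The expected value of d is the true value divided by J, where J(df) = Γ(df/2) / [√(df/2) × Γ((df-1)/2)].

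- J(4) = Γ(2) / [√2 × Γ(1.5)] = 1 / (1.4142 × 0.8862) = 0.798.
- 1/J(4) = 1.253, a mean excess of 25%.
- With four completers (3 df), J(3) = 0.724 and 1/J(3) = 1.382, a mean excess of 38%.

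Simulation with n = 5 (1,000,000 replicates for each correlation) gives 1.25 for both the SD of change and the baseline SD, at every pre/post correlation tried from 0 to 0.95.

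**Mean against median**

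The distribution of d is skewed, so the typical excess is smaller than the mean excess. For a true standardised change of 0.80, the noncentral t distribution gives a mean d of 1.00 and a median of 0.86. The median excess is 0.86/0.80 - 1, or about 7%.

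**Bias with the SD pooled over the two visits** (same simulation)

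| Pre/post correlation | Mean d / true d |
|---|---|
| 0 | 1.11 |
| 0.5 | 1.13 |
| 0.7 | 1.16 |
| 0.9 | 1.20 |
| 0.95 | 1.22 |

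The two visits share the same five people, so their variances are correlated and the pooled SD does not carry a full 8 df unless the correlation is 0. The 8-df factor, J(8) = 0.903, would leave 1.20 × 0.903 = 1.08 at a correlation of 0.9, still about 8% too high on average.

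**Imprecision**

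For the SD of change, t = d√n on 4 df. Inverting the noncentral t gives:

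| Observed d | g = 0.798 × d | 95% CI for the true value |
|---|---|---|
| 0.50 | 0.40 | -0.46 to 1.41 |
| 0.80 | 0.64 | -0.26 to 1.79 |
| 1.00 | 0.80 | -0.14 to 2.07 |

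Bias and noise compare as follows. At a true value of 0.50 the mean bias is 0.50 × 0.253 = 0.13, against a sampling SD of about 0.7. At 0.80 the bias is 0.80 × 0.253 = 0.20, against about 0.82.

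**The case against.** The best defence is that d is a supplementary descriptive statistic. The sentence opens with the word also, it covers one arm only, and the between-group hypotheses are tested by two-sample t-tests that this bias does not touch. The study is openly a pilot limited by funds, the bias is small beside the noise, and anyone who knows n and the standardiser can convert d to g. Some authors also use the name Cohen d loosely for a corrected version.

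Much of this stands, and it limits the point to how the effect sizes are reported. It does not answer the missing standardiser or the missing interval. Without the standardiser a reader cannot make the conversion. That d is uncorrected is inferred from its name and from silence; if a correction is intended, a clause would settle it.

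Three stronger readings are tempting, and the documents do not support them.

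- **That the bias makes the treatment look better.** It multiplies whatever the true change is, so it enlarges decline as much as improvement and adds nothing to a true zero. One of the two planned values comes from an untreated period.
- **That a later trial sized on this d would be 36% too small.** That figure is 1 - J(4)² = 1 - 0.637, which holds only at the mean d. For a true 0.80, the median implied sample size is about 13% too small, and about 46% of samples imply one that is too large. No section says d will size a later trial, and a one-arm pre/post d would not directly size a controlled one.
- **That effect sizes are the study's chief output.** The stated hypotheses rest on between-group tests and correlations, and the SAP omits d.

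**Conclusion.** The point holds as a reporting defect that should be corrected. The planned within-group d is biased away from zero by 25% on average if standardised by the SD of change or the baseline SD with all five people observed, and by about 11% to 20% at correlations of 0 to 0.9 if standardised by an SD pooled over the two visits. These are expected values under normality. They do not measure the error in any one estimate, and the median excess with the SD of change is only about 7% at a true value of 0.80. The absence of an interval is the more serious half: at n = 5, even an observed d of 1.00 leaves zero inside the 95% CI. The t-tests are unaffected.

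**What to change.** Carry the effect-size analysis into the SAP and specify it there:

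1. Name the standardiser: the SD of change or the baseline SD. If the baseline SD is chosen, say whether the week-12-to-week-24 period uses the week-0 or the week-12 SD.
2. Report Hedges g with the factor for the actual df: 0.798 at 4 df, recomputed if there are fewer completers (0.724 at 3 df). Do not use the 8-df factor for a within-group effect size.
3. Give a 95% CI with every effect size. For the SD of change, obtain it by inverting the noncentral t. This interval is already for the true standardised change, so it is not multiplied by the correction factor. The baseline SD needs its own stated interval method.
4. Report the raw mean change with its 95% CI beside each effect size, and label the baseline-to-week-12 value as untreated change.

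This costs a few lines of SAP text and needs no new data. The price to the sponsor is that the reported effect sizes become smaller and visibly imprecise.
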